This project includes the addition of daily and weekly assessments through the MCC app. Questionnaires and speech samples are obtained weekly by the app, and ratings of mood and sleep obtained daily in the FFT-MCC condition and weekly in FFT-Assess. We have minimized the assessments required through the app and estimate that the weekly abbreviated questionnaires and speech samples will average no longer than 15 minutes to complete. We expect that the ease of completing the assessments through a mobile app will lessen the assessment burden. Prior studies using the MCC app ([name] et al., in press) have shown generally good tolerability and compliance with online mood assessments.

POTENTIAL BENEFITS OF THE PROPOSED RESEARCH TO HUMAN SUBJECTS AND OTHERS

Compensation

Families will be compensated up to \$410 over the 6-month study: \$40 for the intake assessment (paid to the parents and separately, the child) and \$25/each for the standard follow-ups at 9, 18 and 27 weeks. Additionally, \$90 is paid to the parent(s) (and separately, \$90 to the child) for completing the weekly mood and sleep ratings and the online speech samples for the 6-month study (Table below). We will pay teens \$4 cash per call up to \$16 per month for use of the app voicemail system; teens in active treatment will be compensated at their next appointment while teens in the follow-up phase will be compensated at their final research assessment. We will reimburse parents for the costs of their on-campus parking (about \$12) for the research visits at baseline, 9, 18 and 27 weeks. Research interviews will be scheduled at the times (for example, after school; immediately following treatment visits) most convenient for the family. If the parents or child decide to stop the study early, they will be paid for those research assessment sessions completed up to that point. Families in the two treatment conditions will be compensated equally.

The table below summarizes the plan of research assessments and payments.

Task	Payment to Family	Approximate time requirement	When paid?
Baseline in-person assessment and MCC questionnaire battery	\$40 to child, \$40 to parents	2.0 hours	After completing baseline assessment
9 Week in-person assessment and MCC questionnaire battery	\$25 to child \$25 to parents	1.5 hours per person	After completing assessment

18 Week in-person assessment and MCC questionnaire battery	\$25 to child \$25 to parents	1.5 hours per person	After completing assessment

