27 Week in-person assessment and MCC questionnaire battery	\$25 to child \$25 to parents	1.5 hours per person	After completing assessment
Weekly MyCoachConnect calls (answering brief questionnaires, providing speech samples)	\$90 to parent(s), \$90 to child; additional payment for calls by teens is \$4 per call up to \$16 per month	6 hours over 6 months	Week 27 (payment proportionate to assessments completed); calls will be paid out at the next in person appointment

The \$90 paid for completing weekly ratings will be dispensed at the end of the study (week 27). It will only be dispensed in full if the participant has completed at least 50% of the required assessments. For example, if they complete 25% of the assessments, they will be paid $\$90 \times .25 = \22.50 ; if they complete 50%, they will be paid \$45. These payment schedules are made clear in the consent and assent forms.

Cost: Benefit Ratio

In our opinion, the benefits of this study to participating families outweigh its risks. All families will receive an 18-week, 12 session course of family psychoeducation about mood disorders (personalized to the symptoms and course trajectories of their adolescent offspring), and family skills training (communication and problem-solving skills). Parents report that specialized treatments for children with mood disturbances are rare in Los Angeles and where they do exist, are often quite expensive. The information obtained from the study may help guide the subsequent care of the child in the community.

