In exploratory analyses, we compared treatment groups on app engagement (frequency of adolescents' and parents' weekly app check-ins), using scaled Poisson regression models (PROC GENMOD in SAS) to account for the skewed distribution of check-in counts. Goodness of fit tests indicated no evidence of overdispersion (Pearson χ^2 , $p=0.5$, deviance $p=0.3$). Within the FFT-MCC group, we used Spearman rank-order correlations to examine whether the proportion of weeks in which adolescents reported use of an FFT skill on the app were associated with changes in PSR depression scores over 27 weeks.

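### The weekly-rating payment gives two answers between 50% and 99% completion, and the $410 family maximum leaves out the teen call payments

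*Protocol*

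**What the plan says.** All payment terms are in the protocol's Compensation section, its payment table and the paragraph below the table.

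- **Total.** "Families will be compensated up to" $410 over the six-month study.
- **Components.** $40 "for the intake assessment (paid to the parents and separately, the child"); $25 to each side at 9, 18 and 27 weeks; and $90 each to parent(s) and child for weekly ratings and speech samples. Teens also receive $4 per call, capped at $16 a month, which the table lists as additional. Parking of about $12 per research visit is reimbursed.
- **How the $90 is earned.** The table says "payment proportionate to assessments completed". The paragraph below says: "It will only be dispensed in full if the participant has completed at least 50% of the required assessments". It then gives two examples: 25% earns $22.50, and "if they complete 50%, they will be paid" $45. It adds that the consent and assent forms make these schedules clear.
- **Parity between arms.** "Families in the two treatment conditions will be compensated equally".
- **Length of the weekly task.** The Compensation section pays for six months of weekly work. The paragraph on MCC weekly online measures places those measures in the 18-week active phase of treatment.
- **Daily ratings.** The section on tolerability of the assessment batteries describes "ratings of mood and sleep obtained daily in the FFT-MCC condition and weekly in FFT-Assess". Nothing states whether the daily ratings count toward the $90.

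**The concern.** A payment rule for minors and their parents should give one amount for a given level of completion, and a stated maximum should be the most a family can receive. Neither holds here. A family reading the 50% sentence would expect the full $90 once half the work is done. A coordinator applying the example or the table would pay half of that.

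The disputed range is a likely one. The only completion rates the protocol predicts, in Hypothesis 1a, are above 70% for adolescents and above 80% for parents. Those are Phase 1 predictions about speech samples, not Phase 2 targets, but they fall inside the range where the rules disagree.

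The stakes are the accuracy of what families are promised and consistent payment from one family to the next. The efficacy analysis is not at stake.

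**Working it through.** **1. Reproduce the stated maximum.** Inputs are from the Compensation text and table.

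- Intake: 2 × $40 = $80
- Follow-ups: 2 people × 3 visits × $25 = $150
- Weekly ratings: 2 × $90 = $180
- Sum: $80 + $150 + $180 = **$410**

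This matches exactly, so the stated figure contains no call payments and no parking. Parking is a reimbursement and is reasonably left out.

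**2. Add the teen call payments at their cap.** The number of payment months is an assumption, because the protocol gives a monthly cap and a 27-week study.

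- 6 months: 6 × $16 = $96; $410 + $96 = **$506** ($96/$410 = 23% above the stated figure)
- 7 months, if 27 weeks touches seven calendar months: 7 × $16 = $112; $410 + $112 = **$522**

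**3. Apply the two readings of the $90 rule.** Proportionate: $90 × proportion completed. Threshold: $90 at 50% or more, otherwise proportionate.

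| Completed | Proportionate | Threshold | Gap per person | Gap, child plus parent(s) |
|---|---|---|---|---|
| 25% | $22.50 | $22.50 | $0 | $0 |
| 50% | $45.00 | $90.00 | $45.00 | $90.00 |
| 75% | $67.50 | $90.00 | $22.50 | $45.00 |
| 100% | $90.00 | $90.00 | $0 | $0 |

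The 25% example fits both readings. The 50% example fits only the proportionate one. The gap is widest at 50% and closes at 100%.

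**4. Examine the denominator.** Suppose each week counts as one unit and a participant completes every week of the 18-week active phase and none after it. Under the proportionate rule:

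- Denominator 18 weeks: $90 × 18/18 = $90
- Denominator 27 weeks: $90 × 18/27 = $60

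The table's time estimate of 6 hours does not settle this. It is 360/27 = 13.3 minutes a week over 27 weeks, or 360/18 = 20 minutes over 18. The first sits better with the protocol's estimate of no more than 15 minutes for weekly questionnaires and speech samples. That leans toward the longer period, but it is an inference and not a definition.

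**The case against.** **The operative rule can be inferred.** The 50% sentence can be read as a necessary condition only, and the table and both worked examples follow proportionate payment. This is fair, and it is why the proportionate rule is the natural one to keep. But on that reading the sentence does nothing, since anyone at 100% has already passed 50%. A condition with no effect will be read as meaning something.

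**The total is only a summary line.** The call payments are itemised nearby and labelled additional, and the total understates what families receive. That limits the harm. It does not make the stated maximum right. The consent and assent forms are not available here, so it cannot be said that families were given the wrong figure.

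**It is late.** The SAP, dated March 2023, is written in the past tense and reports a fit test, so rewording cannot change conduct. This stands. What remains useful is a correct record, including which rule was applied.

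**A stronger reading to resist.** A reader might infer that the $90 has a different base in each arm, because FFT-MCC rates mood and sleep daily, and then that the SAP comparison in which "we compared treatment groups on app engagement" partly reflects pay. The documents do not support this. The payment text names weekly tasks, gives one time estimate for both arms, and says the arms are paid equally. The procedures section says FFT-MCC ratings are obtained weekly as well as daily. Daily ratings have their own reward, the emoji scheme. No text counts them toward the $90. What survives is narrower: the required assessments are never defined, so the protocol does not rule daily ratings in or out.

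**Conclusion.** The point holds in three limited parts.

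1. **Rule.** The $90 payment gives two answers between 50% and 99% completion, differing by at most $45 per person, or $90 for child plus parent(s). Below 50% and at 100% the readings agree.
2. **Maximum.** The $410 is too low by $96 over six payment months ($506), or by $112 if seven months apply ($522). This assumes that the teen reaches the call cap every month, which is what a maximum should assume.
3. **Denominator.** The required assessments are undefined in content and in number of weeks. The 18-week and six-month descriptions can move the proportionate payment from $90 to $60 for the same work, counting each week as one unit.

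The primary analysis of depressive symptoms and the stated power use none of these figures. A reader might conclude that pay and incentives are wrong throughout, or that the engagement comparison is biased. Neither follows: the other itemised amounts are consistent, and an effect on check-in counts would require an arm difference in pay that the documents do not show.

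**What to change.** - Delete or reword the 50% sentence so that the $90 is multiplied by the proportion completed at every level, as the table and example already do.
- Restate the family maximum as $410 plus up to $96 in teen call payments, with the number of payment months given. Say that parking is separate.
- Define the required assessments as the same weekly tasks over the same stated number of weeks in both arms, and say explicitly that daily FFT-MCC ratings do not enter the count. Reconcile the 18-week and six-month descriptions when doing so.
- Check that the consent and assent forms agree with the corrected text.
- Because the SAP indicates that the study has been run, record which rule and denominator were actually used.

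The cost is wording in the protocol and, if needed, the consent documents. The one downside is that participants completing 50% to 99% receive less than under the threshold reading. If any family was told that 50% earns the full amount, that needs to be handled openly and not corrected silently.

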Appendix

DATA SAFETY PLAN

Responsibility for Data Safeguarding

The principal investigators, Drs. [name] and [name], have ultimate responsibility for data safeguarding. All project staff will have completed the CITI IRB training and UC HIPAA training (UCLA personnel) or other HIPAA training (non-UCLA personnel), and will sign a Confidentiality Agreement (in compliance with university policies and procedures to protect the privacy of the research data) for their entire tenure on this project.

Data Storage

Data used as part of this study will be stored primarily on a shared networking server provided by the UCLA Semel Institute. The network server is located in a locked server room and cabinet and complies with UCLA Health data security protocols and is approved for storage of protected health information. The Semel IT administrators perform regular and encrypted backups of the data. The server is protected using standard security practices including being located behind the UCLA firewall, accessible only by designated users from our staff located at UCLA or connected through the UCLA VPN from an offsite location. Data transferred using devices (such as USB drives and laptops) will be encrypted following UCLA Health device encryption policies. Storage and access procedures are in full compliance with UCLA Health data security policies.

Data management, programming support and statistical consulting services

These services will be provided by SISStat, the biostatistics core in the UCLA Semel Institute for Neuroscience and Human Behavior ([name], Director). SISStat is made up of senior consulting faculty from the departments of Biostatistics and Psychiatry, as well as full-time staff statisticians, database and application development programmers, database managers and web designers. Its personnel have extensive experience providing support for multisite studies involving longitudinal trials, including prior studies by the PI. Services for this project will include the creation of a customized online database that will eventually incorporate a randomization system, data dictionary, adverse event reporting system, data entry forms for all clinical and behavioral measures, project management and tracking tools, and a query and dissemination system to control the flow of data and provide information to investigators and the DSMB committee. Development of this customized database is already well underway because the online database for our high-risk early intervention study (MH093676) used many of the same measures.

SISStat databases feature a variety of built-in quality assurance processes including double entry to verify data correctness, automatic logic and range checking, and strict protocols for data confidentiality, transfer, security and backup. All systems and tools are located on a shared networking server at UCLA, are protected by 128 bit SSL (the secure socket layer technology used for sensitive transactions on the web), and feature an hierarchical system of password protected logins, allowing differential access to project team members as appropriate for their

roles. All requests for analysis datasets will be made through the online query system and must be approved by the PI before they are prepared and distributed by SIStat staff.

Databases are backed up daily on the servers and at regular intervals to tape which is stored off site. Snapshots of the datasets distributed for analyses, along with the corresponding queries, will also be permanently preserved. SIStat personnel will perform ongoing quality checks of the database, monitor the data correction process, and assist study staff with all aspects of system usage and other programming and IT needs. They will coordinate with the study's data technicians, responsible for entry of completed paper/pencil forms) to coordinate the timely completion of data deliverables. SIStat will also notify the Research Coordinator when 9-week follow-ups are coming due.

Data Transmittal

Digital audiotapes containing Five-Minute Speech Samples (FMSSs) will be sent to a transcription service affiliated with UCLA that has been chosen because of its consistency with HIPAA and UCLA rules about confidentiality and privacy. Tapes of FMSSs (coded by study ID) will also be transmitted to [name], MSW, a private contractor who will be responsible for coding of expressed emotion. All personal health information will be stripped from the tapes before transmittal. The default mechanism for electronically transferring files includes either sending through encrypted connections (e.g., SSL/SSH/VPN) and/or encrypting files (256-bit AES approved using software that supports .zip format, e.g. WinZip) into a single archive, in compliance with UCLA Health data security policies.

MCC Mobile App

The MCC mobile app (including both patient- and provider-facing versions) was built using the Chorus platform. Chorus is a web application that allows individuals to create websites and mobile apps to collect and display data similar to sites such as SurveyGizmo. Chorus was created by [name] at the Center for Health Services and Society at UCLA and is hosted by a server at that center. It has been approved by the UCLA Office of Information Security for use in research projects including those that collect protected health information. The server is located in a locked server cabinet and server room with access only by Center IT administrators. Data are regularly backed up. All communication to and from the server is encrypted using SSL certificates. The server is used by multiple IRB-approved studies at UCLA. Study staff will be able to export data in comma-separated format (CSV) from Chorus to the study's primary repository (Semel network drive described above) for storage and analysis.

Audit and Monitoring Plans

Speech samples provided by parents and adolescents will be transcribed and reviewed within 3 days of completion. Study staff will screen transcripts for evidence of thoughts of self-harm or of harming others, including child or elder abuse. If study staff detect the presence of these thoughts or statements, we will implement a standardized notification protocol. This includes immediately alerting the PI and co-PI for further review. If warranted, one of the PIs or a covering licensed MD

or psychology PhD will contact the participant. They will leave up to three voicemails and if unable to reach the participant on the same day, they will contact the participant's emergency contact (usually a parent). Once contacted, the staff member will interview the participant to further clarify their risk of self-harm or of harming others. They will determine an intervention as clinically appropriate based on that risk (see Section on Minimizing Risks).

Data Safeguarding: Standard Procedures

UCLA staff will also abide by the basic set of procedures which are generally utilized to protect identifiable private and proprietary data. For each phase of the study, the following procedures will be implemented:

1. Training staff on data sensitivity and data safeguards.
2. Processing sensitive data in a centralized location with established access control procedures.
3. Storing sensitive hardcopy in locked files when not in use.
4. Restricting access to shared disk files through appropriate use of file permissions.
5. Printing sensitive material only when absolutely necessary. When it is necessary, project staff will ensure that an authorized person is at the printer when the sensitive material appears.
6. If it is necessary to transfer materials by mail, we will use certified mail, return receipt requested, for sensitive data or communications; and registered mail for the most sensitive data or communications.
7. Re-training staff and reviewing sensitive data inventory and data safeguards annually.
8. Reporting all serious violations of the Data Safeguarding Plan in writing to the PI, with a copy to the Privacy Resource Office.

DATA SAFETY MONITORING BOARD

This study will have a separate DSMB committee, consisting of a clinical psychiatrist or psychologist, a statistician, and a community stakeholder (e.g., a parent of a child with mood disorder). The PI has already approached several individuals at UCLA and outside UCLA who have agreed to serve on the committee. The purpose of the DSMB is to review the implementation of the human subjects protocol and help assure the safety of participants. The board will review all serious adverse events (e.g., hospitalizations, suicide attempts) and other adverse events (e.g., medication nonadherence, contact with police, school truancy) in relation to treatment phase (psychoeducation, communication skills, problem-solving skills). The DSMB will make recommendations to the NIMH and the University IRBs if it believes that participants are being endangered by the study procedures or the trial should be stopped. It will make recommendations as to ways to improve the quality of care and confidentiality of the participants. As in our prior studies, this study's DSMB will work with the PI to inspect samples of data and help assure the confidentiality, reliability, and validity of the data collection, entry and management process. The DSMB board will meet yearly (or more frequently if warranted) and receive reports from the PIs about study progress and safety issues. The Board will then issue its own reports to the UCLA IRB and the NIMH, along with suggested corrective courses of action.
